The purpose of this study is to determine the feasibility, acceptability and usability, and to assess the safety of use of a VR-based software in health volunteers. Results from this study will be used to inform the design of a future study in hospitalized patients at risk for delirium.

The question that drives this study is:

In healthy volunteers, what is the feasibility of use of the ReCognition VR-based software and what is the acceptability and usability of the software?

OBJECTIVES AND ENDPOINTS

OBJECTIVES	ENDPOINTS	JUSTIFICATION FOR ENDPOINTS
Primary		
The primary objective of this study is to assess the feasibility of VR-based cognitive stimulation exercises in healthy volunteers.	The primary endpoint is use of the ReCognition VR-based software for 20 minutes by 70% of enrolled participants.	It is important to know if participants can complete the exercise since an incomplete experience will prohibit assessment of the other variables to be measured.
Secondary		
The secondary objectives are 
 to determine the acceptability and usability of VR-based cognitive stimulation exercises 	The secondary endpoints are: 
 Acceptability and usability: the proportion of participants with a System Usability Scale (SUS) score >35. 	Successful implementation depends on the acceptability of the intervention and is one of the main factors considered before adopting and

OBJECTIVES	ENDPOINTS	JUSTIFICATION FOR ENDPOINTS
	
 • Proportion of participants who complete the game without any user errors • Number of attempts to complete the game. 	implementing computerized cognitive software.
Tertiary/Exploratory		
Tertiary objectives are to report the safety of VR-based cognitive stimulation exercises in healthy volunteers.	
 • Safety will be assessed using each of the following endpoints: 
 1. Mean change from pre to 10 minutes: 
 a. Heart rate variability: b. Pulse oximetry oxygen saturation (SpO₂) c. Respiratory rate d. Blood pressure 2. Mean change from pre to end of VR session: 
 a. Heart rate variability: b. Pulse oximetry oxygen saturation (SpO₂) c. Respiratory rate d. Blood pressure 	Knowing the proportion of change in these biometric measures will assist in designing future investigation of patients at risk of delirium

3. Background

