Sample size: We will enroll 30 participants: 15 participants who are >18 or up to 35 years of age and 15 participants who are >60 years of age. Results from each age group will be analyzed separately.

Justification of sample size: The study is a feasibility study having the expectation that 70% of participants in each group (>18-35 years of age and >60 years of age) will complete 20 minutes of the ReCognition VR-based exercise and where each group will be evaluated separately. Descriptive statistics will be used to summarize the findings; 15 participants in each group will be recruited. The intent is that this study will provide information for a larger, subsequent clinical trial of patients >60 years old at risk for delirium.

Data and measures to be taken:

The endpoints for this feasibility study are:

Primary – 70% of participants in each group will complete 20 minutes of use of the ReCognition VR-based software (a binary outcome).

[figure not shown]

Figure 1: Describes the system architecture to the observer and healthy participants

Secondary – We will measure the acceptability and usability of the experience based on the proportion of participants with a System Usability Scale (SUS) score >35.

We will report on the proportion of participants who complete the game without any user errors

We will report on the number of attempts each participant uses to complete the game.

We will examine measure that can inform on safety of the experience to be used in the subsequent clinical trial. The measures are:

1. Mean change from pre to 10 minutes of the ReCognition VR-based exercise in:
 - a. Heart rate variability:
 - b. Pulse oximetry oxygen saturation (SpO₂)
 - c. Respiratory rate
 - d. Blood pressure
2. Mean change from pre to end of the ReCognition VR-based exercise in:
 - a. Heart rate variability:
 - b. Pulse oximetry oxygen saturation (SpO₂)
 - c. Respiratory rate
 - d. Blood pressure

We will report the demographic variables of age, sex, race and ethnicity for each group and the clinical characteristics whereby they meet ASA criteria (body mass index, self-reported history of hypertension with active management, drinking status, and smoking status; see Section 9).

Accessing data from medical records:

This feasibility study involves healthy volunteers. No medical records will be reviewed. Medical history will be self-reported.

Data analysis plan:

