The results of this study will be reported using descriptive statistics. Continuous variables will be reported as means with standard deviation or medians and interquartile range contingent on normality of the distribution. Categorical variables will be reported using Chi-square or Fisher's exact test, as appropriate.

5. Study Intervention

1. The healthy participants will be selected from a random population to use the Recognition VR – based cognitive exercise interventions.
2. The study participants will receive a 3D- ReCognition VR-based simulated cognitive exercise program targeting attention, organizing thinking, motor activities, and executive brain functions.
3. The study team will create an order set for the 3-D Recognition VR – based cognitive stimulation exercise sessions to be delivered to the healthy participants who will place virtual reality headsets on themselves.
4. The detail of the software as follows:

3-D Recognition Virtual Reality-Based Simulation Sessions Program:

Software Platform:

Virtual reality platform will consist of

- The virtual reality headsets manufactured by the Oculus Quest 2 glasses (Facebook inc., USA) with stereoscopic vision and stereo sound will be used to show the virtual world to participants.
- Motion Sensor
- Flat Screen TV with Software

The virtual reality headsets manufactured by the Oculus Quest 2 glasses (Facebook inc., USA) with stereoscopic vision and stereo sound will be used to show the virtual reality to study participants. After headset placement, the study participants will be able to follow instructions provided by virtual nurse AVATAR. The participants will receive low cognitive load exercises based on virtual reality techniques, including a relaxed environment, music therapy, time orientation, delivery instructions, and task completion motivation. The exercise task will focus on attention, organized thinking, motor activities, and executive brain functions.

Dosing:

The study participants will receive approximately 20 minutes of VR- based cognitive stimulation session and fill out a post-user survey.

The session will provide neurocognitive stimulation, engagement through exercise.

The physiological data of vital signs will be recorded before, during, and after sessions (see Schedule of Activities).

Acceptability Survey:

PI or a research team member will interview the healthy participants using the System Usability Scale survey.

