This study will be a single-center study of healthy volunteers conducted at Houston Methodist Hospital. We will enroll 15 participants who are >18 and <35 years of age and 15 participants who are ≥60 years of age. The rationale for the age distribution is to obtain information from people who are considered healthy by ASA criteria 1 and people who meet ASA criteria 2. Participants who are >18 to 35 years of age are a) more likely to have experienced VR software previously and b) more likely to meet ASA criteria 1. Participants who are >60 years of age are a) less likely to have experienced VR software previously and b) more likely to meet ASA criteria 2. These older participants are considered similar to the target population of a proposed subsequent conventional clinical trial; however, it is possible that participants in the younger age group (>18 to 35 years of age) may meet ASA criteria 2.

A total of 30 participants will be prospectively enrolled. All participants will be given post-use surveys to assess usability and efficacy outcomes.

Inclusion Criteria:

1. Healthy volunteers >18 years of age who meet one of the following criteria:
 - a. **ASA 1:** A normal healthy patient. Example: Fit, nonobese (BMI under 30), a nonsmoking patient with good exercise tolerance.
 - b. **ASA 2:** A patient with mild systemic disease. Example: Patient with no functional limitations and a well-controlled disease (eg, treated hypertension, obesity with BMI under 35, frequent social drinker, but is nonsmoking).
2. Person without underlying cognitive disorder or associated phobias (eg. claustrophobia).

Exclusion Criteria:

1. Person with active psychiatry disorders, especially schizophrenia
2. Person who is deaf or blind.

11. Screening and Recruitment

All participants will be screened by the principal investigator and clinical research staff, who have been trained in the clinical investigational plan, to determine if the potential participant is eligible for enrollment. Potential participants will be assigned a screening number which will be recorded in an excel sheet; all participants who receive the study intervention during the study will be noted. All participants must meet eligibility criteria (and if not, which eligibility criteria were not met will be recorded); reasons for not meeting enrollment criteria or receiving study intervention will be recorded. No participants belonging to a vulnerable population will be enrolled.

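### The safety endpoints are defined as mean changes, but the data analysis plan, read literally, may report them only as medians

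*Combined protocol and SAP*

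**What the plan says.** The endpoint table in section 2 lists safety under the tertiary/exploratory objectives, as changes in heart rate variability, SpO2, respiratory rate and blood pressure over two windows. One window is worded "Mean change from pre to end of VR session". Section 4 (Data and measures to be taken) repeats the definitions: "Mean change from pre to 10 minutes of the ReCognition VR-based exercise in" and "Mean change from pre to end of the ReCognition VR-based exercise in" the same four measures.

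The data analysis plan at the end of section 4 has one rule for continuous data: "Continuous variables will be reported as means with standard deviation or medians and interquartile range contingent on normality of the distribution". The study is declared descriptive.

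On the groups, section 4 says "15 participants in each group will be recruited" and "Results from each age group will be analyzed separately". On purpose, the justification column in section 2 says: "Knowing the proportion of change in these biometric measures will assist in designing future investigation of patients at risk of delirium".

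No section says which wording governs the safety changes, how normality is to be judged, at what level (per group or pooled), or that both groups must receive the same summary.

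**The concern.** The endpoint definition fixes the quantity in advance: a mean. The analysis rule lets the observed data choose between a mean and a median. Where the data look non-normal, following the rule as written produces a number that is not the named endpoint, and the mean and SD need not appear at all.

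This matters mainly because the changes are collected to help plan a later trial. A planner will want the mean change and its SD in the older group. A median with an IQR from 15 people is a poor substitute, and if the choice is made group by group, one variable may carry different summaries in the two age groups.

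There is also a safety aspect. When most participants do not change and a few worsen, the data are non-normal, so the rule selects the median. The median is the summary least sensitive to those few.

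**Working it through.** **The plan's own figures.** No alpha, power, SD or effect size is given, so no calculation behind 15 per group can be reproduced. The only check available is 15 + 15 = 30, which agrees with section 10 ("A total of 30 participants will be prospectively enrolled").

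**The texts side by side.** Endpoint: mean change, four measures, two windows (sections 2 and 4). Reporting rule: mean (SD) or median (IQR), depending on normality, with no variable exempt (section 4). The two agree only if every change is judged normal.

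**How often the switch could occur.** The documents give none of the following, so all are assumptions: normality is judged per group, by Shapiro-Wilk at 5%, with SpO2 read in whole percent, and with the distributions listed. Samples of 15 were simulated. Let p be the share rejected. If both groups share one distribution and are independent, the chance that they get different summaries is 2p(1 − p).

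| Assumed distribution of the variable | p | 2p(1 − p) |
|---|---|---|
| Normal | 5% | 2 × 0.05 × 0.95 = 10% |
| Lognormal, sigma 0.5 | 39% | 2 × 0.39 × 0.61 = 48% |
| SpO2 change, mean −0.5, SD 1, rounded | 56% | 2 × 0.56 × 0.44 = 49% |
| Same, SD 1.5 | 22% | 2 × 0.22 × 0.78 = 34% |
| Same, SD 2 | 14% | 2 × 0.14 × 0.86 = 24% |
| Same, SD 3 | 8% | 2 × 0.08 × 0.92 = 15% |

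The SpO2 rate depends heavily on the SD, because it is mostly rounding that trips the test. No single figure should be quoted without the range.

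**What a minority fall looks like.** Take 12 of 15 unchanged and 3 falling by 5 points.
- Mean = (12 × 0 + 3 × (−5)) / 15 = −1.0.
- SD = √[(12 × 1² + 3 × 4²) / 14] = √(60/14) = 2.07.
- Median 0, IQR 0 to 0; Shapiro-Wilk p < 0.001, so the rule reports the median and IQR.
- A 95% interval for the mean has half-width t(0.975, 14)/√15 = 2.145/3.873 = 0.554 SD. Here 0.554 × 2.07 = 1.15, giving −2.15 to 0.15.

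**How general that example is.** Suppose each participant independently has a 20%, 30%, 40% or 45% chance of falling by 1 to 4 points and otherwise does not change.
- The rule selects the median, and that median is 0, in 99.6%, 95%, 79% and 66% of samples.
- The lower quartile is also 0, so that the IQR hides the fall too, in 65%, 29%, 9% and 4%.

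Under the symmetric rounded model with mean −0.5 and SD 1, a median of 0 is reported in about 28% of samples, and the lower quartile is also 0 in only about 1%. Masking is therefore mainly a feature of falls confined to a few people. A more widespread fall usually shows in the IQR.

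**The case against.** The strongest reply is that the specific governs the general. The safety endpoints are expressly named as mean changes, and the sentence in the analysis plan is a general one that also covers age, body mass index and number of attempts. On that reading the mean change would be reported anyway. This is at least as natural as the literal reading, and it defeats the stronger inference that the analysis rule overrides the endpoint definitions: the documents state no precedence. What stands is that they leave the matter open.

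A reader might also infer that the switch is made separately in each group. Separate analysis of the groups makes that plausible, but no level and no formal test are stated, so the rates above are conditional.

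A reader might infer that a real SpO2 fall will be reported as zero. That is possible but depends on the model, as the calculations show. Section 14 also reports adverse events as a proportion of participants, with an SpO2 threshold of 88% and a criterion of more than 20% change from baseline. That catches large falls. A 5-point fall from an illustrative 97% reaches 92%, a relative change of 5/97 = 5.2%, and meets neither. Nor does a mean alone reveal how many fell, which is a reason to show both summaries and the range.

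Finally, the plan proposes no between-group comparison of these changes, and the later trial concerns patients over 60. Mismatched summaries are therefore an inconvenience and do not invalidate a planned analysis. The absence of confidence intervals is not an error in a descriptive exploratory analysis, and where n, mean and SD are shown a reader can compute them.

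**Conclusion.** The point holds as an unresolved conflict of minor severity. The endpoint definitions call for a mean change, while the reporting rule, taken as written, allows a median to replace it. That the conflict exists rests on the text alone. Its size rests on the assumed test, its 5% level, per-group application and the assumed distributions: the switch would occur in about 5% of normal samples, 39% of lognormal samples with sigma 0.5, and 56% down to 8% of whole-number SpO2 changes as the SD goes from 1 to 3.

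The documents do not support saying that the endpoints are overridden, that the two groups will be summarised differently, or that a fall in SpO2 will be concealed. Each of these may happen. The affected endpoints are tertiary/exploratory, and the primary completion proportion and the SUS proportion are untouched.

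**What to change.** Replace the sentence on continuous variables in the data analysis plan with wording such as: *For every continuous variable, in both age groups and at every time point, n, mean, SD, median, IQR, minimum and maximum will be reported. The safety endpoints will always be reported as mean change from pre with SD. No judgement of normality decides which summary is shown.*

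A 95% confidence interval for each mean change would be a useful addition, since it tells the planner of the next trial how precise 15 observations are.

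The cost is one sentence and a wider table. No new data, participants or procedures are needed.

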Only the minimum amount of personal information needed to conduct this study will be collected regarding participants' privacy interests. Study participants will be informed that the only individuals who can see un-coded personal health information include the following: the Study Doctor, other employees who work on this study (including the Institutional Review Board) at the hospital, employees of the sponsor who check that this study is being done correctly, and regulatory authorities where required by law. In addition, participants will be carefully informed about the Release of Health Information section in the ICF, which describes who will access their information and how it will be used. We will emphasize that participation in this study is voluntary and that participants can choose at any time to cease participation and revoke authorization to use and disclose their information.

14. Risks to Subjects

The risks below are associated with the use of the Oculus Quest 2 Virtual Reality Headset Device.

All adverse events (AEs) will be captured, and recorded at each time point. We will report AEs as a proportion of study participants who developed AEs.

Specific AEs to be monitored will include:

Neurological AEs: (defined as new-onset blurry vision, tingling, perioral numbness, seizures, or coma within 30 minutes after starting the study intervention)

Cardiovascular AEs: (defined as new-onset hypotension [SBP <90 mmHg and DBP <60 mmHg], bradycardia [HR < 50 bpm], tachycardia [HR >130 bsspm], or any new hemodynamic instability requiring more than two vasopressors after starting the study interventions

Pulmonary AEs: (defined as new-onset hypoxia [SpO2 < 88%] and/or hypercarbia [PCO2 > 60 mmHg] on arterial blood gas within 30 minutes of starting study interventions

Cardiac Adverse Events: New-onset hypotension (SBP <90 mmHg and DBP <60 mmHg), Bradycardia (HR < 50), Tachycardia (HR> 100), and Arrhythmias (Supraventricular or ventricular) with HR> 150 beats per minutes within 5 minutes after the starting of 3D Simulated VR sessions. Or changes >20% from baselines.

Pulmonary Adverse Events: New-onset hypoxia: SpO2 < 88%, Respirator rate > 35 breaths/minute within 5 minutes after the starting of 3D Simulated VR sessions.

Others:Rash, nystagmus, muscular hypertonicity, clonus or myoclonic jerks, and allergic reactions

If enrolled participants vital signs changes > 20% from baseline, the session will be stopped as it would be considered unsafe events

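### The only method named for categorical variables is a between-group test, which does not fit a plan to describe each age group's completion against 70%, and no confidence interval is specified

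*Combined protocol and SAP*

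**What the plan says.** The data analysis plan at the end of Section 4 is three sentences long. The first sets the approach: "The results of this study will be reported using descriptive statistics". The second names summaries for continuous variables: mean and SD, or median and IQR. The third covers everything categorical: "Categorical variables will be reported using Chi-square or" Fisher's exact test, whichever suits. It names no count, percentage or interval.

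The outcomes to which that third sentence would apply are defined elsewhere:

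- **Primary endpoint, Section 4:** "70% of participants in each group will complete 20 minutes of use of the ReCognition VR-based software (a binary outcome"). The objectives table in Section 2 words it for the whole sample: "The primary endpoint is use of the ReCognition VR-based software for 20 minutes by 70% of enrolled participants".
- **Secondary endpoints, Sections 2 and 4:** the proportion with a SUS score above 35, and the proportion completing the game without user errors.
- **Adverse events, Section 14:** "We will report AEs as a proportion of study participants who developed AEs".

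On the age groups, the sample size paragraph of Section 4 says "Results from each age group will be analyzed separately", and the justification that follows it repeats the point. No objective in Section 2 compares younger with older participants. No confidence interval for a proportion appears anywhere in the document.

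**The concern.** Fisher's exact test, and the chi-square test of association usually paired with it, ask whether two groups differ. The protocol asks something else: what proportion of each group completes 20 minutes, and how that proportion stands relative to 70%. The one specific instruction for categorical data therefore serves a comparison that the protocol does not plan, and it sits awkwardly beside the descriptive, group-by-group intent stated in the same section.

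The missing interval matters because of what the results are for. They are meant to inform a later trial in patients over 60 at risk of delirium, so the older group's completion and adverse event proportions will be carried forward. From 15 people, a bare percentage, or a statement that no adverse events occurred, looks much firmer than it is. Nothing in the plan requires the uncertainty to be shown.

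**Working it through.** **Inputs.** There are 15 participants per group and 30 in total, with a target of 70% in each group (Section 4). The protocol gives no confidence level, significance level or precision target, so there is no planned figure to reproduce. The 95% level used here is an assumption.

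**Step 1: the count that meets the target.** 0.70 × 15 = 10.5, so 11/15 (73.3%) is the smallest count that meets 70%, and 10/15 (66.7%) misses it.

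**Step 2: what the named test returns.** Two-sided Fisher p-values for younger versus older:

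| Group 1 | Group 2 | Position relative to 70% | Fisher p |
|---|---|---|---|
| 11/15 | 11/15 | both meet | 1.00 |
| 6/15 | 6/15 | both miss | 1.00 |
| 11/15 | 10/15 | one meets, one misses | 1.00 |
| 15/15 | 10/15 | one meets, one misses | 0.042 |

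In the first three rows the observed table is a most probable one given its margins, so p = 1. In the last row all 5 non-completers fall in one group, and p = 2 × C(15,5)/C(30,5) = 2 × 3003/142506 = 0.042. The same p-value thus goes with success in both groups, failure in both, or one of each. A small p-value shows that the groups differ but not how either stands against 70%.

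**Step 3: what an interval would show.** For x events in n, the exact (Clopper-Pearson) 95% limits are the 0.025 quantile of Beta(x, n − x + 1) and the 0.975 quantile of Beta(x + 1, n − x). When x = 0 the lower limit is 0 and the upper limit is 1 − 0.025^(1/n).

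| Result | Estimate | Exact 95% interval |
|---|---|---|
| 10/15 | 66.7% | 38.4% to 88.2% |
| 11/15 | 73.3% | 44.9% to 92.2% |
| 14/15 | 93.3% | 68.1% to 99.8% |
| 15/15 | 100% | 78.2% to 100% |
| 0/15 adverse events | 0% | 0% to 21.8% |
| 0/30 adverse events | 0% | 0% to 11.6% |

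For the zero counts, 1 − 0.025^(1/15) = 0.218 and 1 − 0.025^(1/30) = 0.116.

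The intervals for 10/15 and 11/15 overlap almost entirely, although one result misses the target and the other meets it. Only 15/15 has a lower limit above 70%. The interval is therefore a statement of precision and should not be turned into the pass rule; the target as written concerns the observed proportion.

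**The case against.** The strongest reply is that the plan, read as a whole, already gives the answer. Section 4 twice calls for descriptive statistics, Sections 2 and 4 define the SUS and error-free outcomes as proportions, and Section 14 promises a proportion for adverse events. Comparing x/15 with 70% needs no test. The sentence at issue does not mention the primary endpoint, and it also covers sex, race and other baseline variables. A feasibility study declared to be descriptive is not invalid for want of an interval, which any reader could compute from x/15.

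Most of this stands, and it limits the point. A reader might infer that the primary question would go unanswered, or that adverse events would be reported only as a p-value. The documents do not support either inference: the proportions are promised, and nothing proposes judging 70% by a younger-versus-older p-value. A reader might also object that a between-group test would be underpowered. The protocol gives no pair of rates to compare and plans no such comparison, so a power figure would rest on invented inputs.

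It is also true that a chi-square test can be run on one sample against 70%. The protocol does not describe that use, and with 0.30 × 15 = 4.5 expected non-completers the usual minimum of 5 is not met.

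Two things remain. The only specific instruction for categorical variables names tests where counts and percentages belong, and the primary endpoint is categorical by the protocol's own description. No measure of uncertainty is required for any proportion. That the study is descriptive argues for replacing tests with estimates, not for keeping the sentence.

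**Conclusion.** The point holds as a mismatch of method and a missing interval, not as a missing estimate. The chi-square/Fisher sentence conflicts with the plan's own descriptive, per-group intent and cannot show how a group stands against 70%. The unreported uncertainty is large: a group that just meets the target at 11/15 has an interval from 45% to 92%, and no adverse events in a group of 15 leaves rates up to 21.8% open. These limits rest on an assumed 95% level, the Clopper-Pearson method and all 15 participants being counted. A Wilson interval would be somewhat narrower for 11/15 (48% to 89%) without changing the conclusion. The data stay fully analysable, so this is a modest correction that should be made before analysis.

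**What to change.** Replace the third sentence of the data analysis plan with wording such as: *Categorical variables, including the primary endpoint, SUS >35, error-free completion and AEs, will be reported in each age group as n/N and percentage with an exact (Clopper-Pearson) 95% confidence interval.* Then:

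- Use all enrolled participants as the denominator for the primary endpoint, and state N for the other outcomes. Reconcile this with Section 12, under which withdrawn participants' data are removed.
- State that the 70% target is met in a group at 11 or more of 15, and align the whole-sample wording in Section 2 with the per-group wording in Section 4.
- Delete the chi-square and Fisher tests, or name the between-group comparison they serve and label it exploratory.
- If adverse events are also pooled over all 30, label that a supplementary summary, since the groups are otherwise analysed separately.

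The cost is a few sentences and no new data. The one drawback is that the results will look less certain than bare percentages.

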Attention is the most crucial cognitive domain required for the effective completion of mentally challenging tasks by healthy individuals. Many healthy people cannot complete high executive brain functioning tasks due to lack of focus or attention, leading to poor performance both at work and home. Generally, mild attention deficit is not identified, and daily life stresses are usually blamed. Computerized cognitive training programs have shown improved attention deficit disorder and mild cognitive impairment. Virtual Reality (VR) is an emerging technology and can improve brain functions, including attention. VR engages multiple learning systems, making it a more effective natural environment for cognitive training. Based on this idea, our team developed a 3D simulated software platform prototype called ReCognition VR with incorporated exercise in the forms of games that can improve attention and executive functions.

Recognition VR software (Figure 1) allows users to immerse themselves in a relaxing virtual environment; reorient the user to person, time, and location; and play mini-games to encourage attention, focus, and movement of limbs; and record user progress and scores in mini-games.

Critical gaps exist in our knowledge of cognitive interventions and their application through VR. Data on interventions focused on early cognitive exercise using Virtual Reality Simulation, specifically using Oculus Quest 2 and Unity software, are limited. Moreover, many critical barriers to implementing cognitive exercise in clinical protocols exist. Cognitive stimulation through VR is a new and upcoming area in technology that is rapidly expanding but currently limited in the literature. A lack of understanding or appreciation for the evidence supporting cognitive stimulation through VR, specifically gamification, contributes to the barriers. The rapid increase and use of VR in other areas urges our team to seek this area for development.

The major goals of this proposal are to assess the feasibility and usability of VR-based cognitive interventions in healthy volunteers using ReCognition VR software while providing easy delivery of cognitive stimulation exercises provided by VR.

4. Study Design

The study is a single-center, prospective assessment of the feasibility, acceptability and usability of ReCognition VR -based simulated cognitive stimulation to improve attention and focus in healthy participants.

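### The SUS is to be collected by interview with the team that built the software, other passages describe the survey differently, and only the share scoring above 35 is a named endpoint

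*Combined protocol and SAP*

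**What the plan says.** **Mode of collection.** Under Acceptability Survey, Section 5 says the "PI or a research team member will interview the healthy participants using the System Usability Scale survey". Under Dosing, the same section has participants receive a VR-based "cognitive stimulation session and fill out a post-user survey", without naming that survey. The schedule of activities has a single survey row, called System User Survey, at the end of study on Day 1. Section 10 says all participants are given post-use surveys, in the plural, covering usability and efficacy. The identifier table in Section 8 records phone numbers because they are needed for a questionnaire.

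**Who made the product.** Section 3 states that "our team developed a 3D simulated software platform prototype called ReCognition VR", and Section 1 says the same in similar terms.

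**Endpoint.** Sections 2 and 4 define acceptability and usability through the "proportion of participants with a System Usability Scale (SUS) score >35". No section gives a minimum, a maximum or a scoring rule. Section 4 adds "Results from each age group will be analyzed separately", with 15 participants per group. Its data analysis plan says "Continuous variables will be reported as means with standard deviation or medians and interquartile range contingent on normality of the distribution", but does not mention the SUS.

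**Use of the result.** Section 2 says "Successful implementation depends on the acceptability of the intervention" and "Results from this study will be used to inform the design of a future study".

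**The concern.** Usability and acceptability are in the study title, the hypothesis and the driving question. The SUS is a self-report of opinion, so how it is asked is part of the measurement. A participant who has just been shown a prototype and is then questioned about it by the team behind it may answer politely. The study has no comparison arm against which a shared upward shift would cancel, and the level of the ratings is itself the result to be carried into the next study. If the mode is left open, some participants may be interviewed and others may fill in the form, and the scores would then not be comparable.

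The second issue is what is kept from the scores. A cut turns each score into a yes or no, so a score just above 35 and one near the top of the scale count alike. With 15 per group there is little information to spare, and without a stated range a reader cannot tell whether passing 35 is easy or hard.

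**Working it through.** **1. The survey statements side by side**

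| Place | Instrument | Mode |
|---|---|---|
| Section 5, Acceptability Survey | SUS | Interview by the PI or a team member |
| Section 5, Dosing | Unnamed post-session survey | Filled in by the participant |
| Section 5, schedule | One row, System User Survey | Not stated |
| Section 8, identifier table | Unnamed questionnaire | Phone number said to be needed |
| Section 10 | Surveys (plural), usability and efficacy | Given to participants; mode not stated |

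The single schedule row suggests that the Dosing survey is the SUS, in which case the two statements in Section 5 disagree on mode. The plural in Section 10 leaves room for a second instrument. The phone entry may relate to the telephone safety follow-up in Section 17, but the table does not say so. No statement provides for an interviewer outside the team.

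**2. What can be reproduced.** The sample size adds up: 15 + 15 = 30. The cut of 35 has no derivation in the documents, so there is nothing to reproduce.

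**3. Precision of the proportion, n = 15 (exact Clopper-Pearson 95% interval)**

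- 15/15: 78.2% to 100%. The lower limit is 0.025^(1/15) = 0.782.
- 14/15: 68.1% to 99.8%.
- 11/15: 44.9% to 92.2%.

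**4. Precision of the mean, n = 15.** The half-width is t(14; 0.975) × SD/√15 = 2.145/3.873 × SD = 0.554 SD. For assumed SDs of 10, 15 and 20 points on a 0-100 equivalent scale this is 5.5, 8.3 and 11.1 points.

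**5. Where 35 lies.** The position is (35 − min)/(max − min). The ranges are assumptions; none is in the documents.

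- 0-100: 35/100 = 35%.
- 10-50: 25/40 = 62.5%.
- 0-40: 35/40 = 87.5%.

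A midpoint score passes on 0-100 (50) but fails on 10-50 (30) and on 0-40 (20).

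**6. Illustration only.** Assume normal scores with SD 15 in 0-100 equivalents. The expected count above the cut is 15 × [1 − Φ((c − mean)/15)], with c = 35, 62.5 or 87.5.

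| Mean | 0-100 | 10-50 | 0-40 |
|---|---|---|---|
| 60 | 14.3 | 6.5 | 0.5 |
| 70 | 14.9 | 10.4 | 1.8 |
| 80 | 15.0 | 13.2 | 4.6 |

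Moving the mean from 60 to 80 changes the expected count by 0.7, 6.7 or 4.1 participants, depending on the scale. The model is unbounded: at mean 80, 1 − Φ(20/15) = 9.1% of modelled scores exceed the maximum. That is about 1.4 of the 4.6 participants in the last cell. The table shows only that a count above 35 is hard to read alone; it estimates nothing about this study.

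**The case against.** The strongest reply is that the bias is an inference. Any research team member may do the interview, and Section 1 lists a neurologist, a statistician and a student, so the interviewer need not have built anything. Interviewing is also a legitimate choice where half the sample is in the older group and may need help. This stands as far as it goes: a reader might infer that the developers collect their own ratings and that the scores will be inflated, but the documents establish neither. They do permit it, and they include no safeguard.

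A reader might also infer that Section 5 flatly contradicts itself. That is too strong, because Section 10 leaves open that the survey filled in is not the SUS, or not only the SUS. The wording is unreconciled rather than shown to be contradictory.

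Third, the general sentence on continuous variables, with the separate analysis by age group, may already cover a summary of the SUS total. That is a fair reading. But both endpoint statements name only the proportion, so the summary is not assured, and no interval is planned for either.

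Last, a plan need not reprint the scoring of a named instrument. True, but here the endpoint depends on a specific number, and that number cannot be interpreted without its range.

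**Conclusion.** The point holds in a limited form. The mode of SUS collection is not settled across Sections 5, 8 and 10. The one statement that names the SUS and a mode has the product's own team ask the questions. This is an avoidable risk of favourable answers, of a size that the documents cannot give. Defining the endpoint only as the share above 35 discards information at 15 per group, where even 14/15 is compatible with anything from 68.1% to 99.8%.

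It would be tempting to call the cut of 35 too lenient or too strict. The documents support neither, since it lies anywhere from 35% to 87.5% of the way up the three ranges assumed here. How much the proportion loses compared with the total likewise depends on the scale and on where the scores fall.

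The endpoint is secondary and descriptive. The primary endpoint, completion of 20 minutes, and the sample size are not affected. The change is worth making because it costs little and because the mode cannot be corrected once the scores have been collected.

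**What to change.** 1. In Section 5, make the SUS self-completed, on paper or in the REDCap system already planned. Limit staff help to the mechanics of the form, and record which participants were helped.
2. Reconcile the survey wording in Section 5 (Dosing, Acceptability Survey and schedule), Section 8 (identifier table) and Section 10. Say whether there is one instrument or more, and name each one wherever it appears.
3. In Sections 2 and 4, report the SUS total per age group as mean (SD) or median (IQR) with a 95% confidence interval, beside the proportion above 35 with its exact 95% interval.
4. State the scoring range to which 35 refers.

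The cost is wording in Sections 2, 4, 5, 8 and 10, with no added visits or participants. There are two downsides: some older participants may need help with the form, and the ratings may come out less favourable than in an interview.
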